#### 6.2.1.12 Glucose

In children, hyperglycemia and insulin resistance are associated with the metabolic syndrome, a cluster of risk factors strongly linked to CKD and CVD. Serum glucose will be measured centrally and locally at baseline and at all annual visits. Pending ancillary funding, we will measure fasting insulin levels to allow for an estimation of insulin resistance.

## 6.2.1.13 Urine Pregnancy Test

Urine pregnancy test, Human Chorionic Gonadotropin (HCG) will be assessed locally at the first baseline visit (V1a) and at annual follow-up visits for females of child-bearing potential (post menarche). Positive tests will result in the participant no longer completing regular CKiD study visits; however, participants with positive results will be given the option to participate in the continued follow-up protocol. In addition, testing will be done in accordance with local IRB requirements or investigator preference. Sites should contact local institutions and state regulations to determine how to handle positive pregnancy tests.

#### 6.2.1.14 Surplus of Serum at CBL

In the event that there is a surplus of serum at the CBL after the centrally analyzed tests are completed and pending additional funding, the left over serum will be used to perform additional studies such as hepcidin, 1,25 vitamin D, FGF-23, beta-Trace protein and magnesium.

## 6.2.1.15 Tests Performed Locally

In addition to the samples sent to the Central Biochemistry Laboratory, a renal panel will be performed locally for all study participants. If lab results are needed immediately for clinical care, they should be obtained locally. Only the results for tests performed by the Central Biochemistry Laboratory will be available on NEPHRON, the data management system, located at https://statepiaps6.jhsph.edu/nephron/groups/aspproc/.

## 6.2.2 Non-Core Tests for Post RRT Protocol Participants

## 6.2.2.1 Twenty-Four Hour Urine Collection

At selected sites, a 24 hour urine collection will be obtained in peritoneal dialysis participants at post-RRT baseline and annual study visits. Urine collection should only be obtained from those participants who are toilet trained and are able to voluntarily collect the urine. No participants should be catheterized for the urine. Also, urine samples will not be collected for participants who are incontinent at night or in diapers.

#### 6.2.2.2 Kt/V

Kt/V is a formula used to quantify hemodialysis and peritoneal dialysis treatment adequacy. At selected sites, locally calculated Kt/V values will be obtained in dialyzed participants at post-RRT baseline and annual study visits. For hemodialysis treatment participants, we will obtain Kt/V values locally calculated within the 30 days prior to the study visits. For peritoneal dialysis treatment participants, we will obtain Kt/V values (dialysis and urine) locally calculated within the 6 months prior to the study visits.

#### 6.2.3 Outcome Measures

#### 6.2.3.1 Primary Outcome Measures

The primary renal outcomes will be the GFR level and slope, as measured by iohexol GFR. Methods for the analysis of these outcomes as continuous variables will be implemented (see section 8). For clinically meaningful cut-off values (e.g., slope per year greater than 10 ml/min) we will use methods appropriate for the analysis of binary outcomes.

#### 6.2.3.2 Secondary Outcome Measures

6.2.3.2.1 Onset of ESRD (start of chronic dialysis or renal transplantation) or development of GFR <15 ml/min/1.73m^2. This will be a time-to-event analysis. It will be important to consider GFR at entry into the cohort study by stratification or multivariate analysis.

6.2.3.2.2 "Significant loss of renal function" defined as 50% decline or 25 ml/min/1.73m^2 decline in GFR from baseline. This will also be a time-to-event analysis that needs to take into account baseline GFR.

6.2.3.2.3 Composite clinical outcome defined by the occurrence of either a 50% decline, or a 25 ml/min/1.73m^2 decline in GFR from baseline, or onset of ESRD.

6.2.3.2.4 Slope of change in proteinuria over time as assessed by a spot urine protein/urine Creatinine ratio (UP/Cr). We will also assess for new overt proteinuria – UP/Cr > 0.2 (or >4 mg/m^2/hr of proteinuria).

6.2.3.2.5 All-cause death will be captured as an end point. Although very uncommon in children with CKD, we will monitor for this outcome. "Renal specific death" is difficult to define, and would be even more unlikely in children, as few patients die directly of renal disease.

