In Cohorts 1 and 2, children less than one year old were not enrolled; however, in cohort 3 we will focus on enrolling children close to their onset of kidney disease. Therefore, we will enroll children as young as 6 months old. The upper limit of 16 years was chosen to optimize follow-up for all subjects to be followed for at least four years, since the subjects would likely remain under the care of the pediatric nephrology centers enrolling patients.

Based on estimates from both CCCs, in Cohort 1 we expected 56% Caucasian, 24% African-American, 15% Hispanic, and 5% Asian, Pacific Islander, American Indian, or other, and we placed an upper limit of 65% for the percent of the cohort that would be Caucasian. In Cohort 1, 37% of children with glomerular disease were African-American. Since the study expected to enroll a higher proportion of children with glomerular disease in Cohort 2, it was also expected that there would be more African-American children enrolled resulting in more generalizable study population. However, there were similar percentages of African-Americans enrolled in both cohort, 23% and 20% respectively. In Cohort 3, we expect to enroll a similar percentage of African-Americans and we will place an upper limit of 65% for Caucasian enrollment. Also, based on estimates from the east coast CCC, we expect that overall 40% of the combined cohort will be female.

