Eligibility for Cohort 3 will be determined by having a Non-Glomerular diagnosis of CKD whose duration is less than 5 years at date of enrollment and age between 6 months to 16 years old. In order to assure that CKD is present, for specific non-glomerular diagnoses, we will require two or more of the following: 1) urine protein to creatinine ratio greater than 0.5 for children less than 2 years old, or urine protein to creatinine ratio greater than 0.2 for children 2 years of age and older; 2) hematuria (for at least 3 months): 3) evidence of renal tubular disorders; 4) abnormalities detected by kidney biopsy or imaging (bilateral disease or solitary kidney disease); 5) a serum creatinine measurement greater than 0.4mg/dL for children less than 2 years old, or, for children 2 years of age and older, an estimated Glomerular Filtration Rate (eGFR) less than 90 ml/min|1.73m^2 based on the updated Schwartz formula; or 6) hypertension defined by documented note in medical record, current treatment of hypertension, or blood pressure > 95th percentile on at least two occasions. Additionally, these conditions must have occurred after the initial 6 months of life (with the exception of abnormalities detected by kidney biopsy or imaging) and must not be secondary to a current or resolving episode of acute kidney injury. Since description of course to renal replacement therapy is of primary interest, children who are expected to receive renal replacement therapy within 6 months of date of enrollment will not be recruited. Eligible children must be willing to complete baseline and follow-up testing, and all procedures at scheduled annual visits for the duration of the study. Spanish-speaking children and children who are blind and/or deaf who meet the inclusion criteria will be eligible for study participation if they are able to complete either the neurocognitive or behavioral assessments of the neuropsychological component and all other study procedures. Since retention in a cohort study is of central importance, numerous efforts will be employed to include in the cohort children with the highest likelihood of participation in the study for the long term. Also, children can be included in the study only if they and their parents/legal guardians are willing and able to provide informed consent and assent.

In summary, the following conditions comprise the inclusion criteria:

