- Age between 1 and 16 years (before 17th birthday) for Cohorts 1 and 2; age between 6 months and 16 years (before 17th birthday) for Cohort 3
- Estimated (based on Scr) Schwartz GFR between 30 and 90 ml/min|1.73m^2 for Cohort 1 OR an estimated GFR between 45 and 90 ml/min|1.73m^2 based on the updated Schwartz formula for Cohort 2
- Willingness and ability to provide informed consent and assent
- For Cohort 2, an equal distribution of children with glomerular and nonglomerular causes of disease were enrolled (i.e., 150 within each) and the study placed an upper limit of 60% for the percent of enrolled with nonglomerular disease.

• For Cohort 3, 190 children with non-glomerular diagnosis and duration of kidney disease less than 5 years will be enrolled.

Patients with the non-glomerular diagnoses listed below that meet the initial criteria (i.e., duration of kidney disease less than 5 years, and age between 6 months and 16 years old) are eligible and do not have to meet additional criteria:

- Branchio-oto-Renal Disease/Syndrome
- Cystinosis
- Medullary cystic disease/ juvenile nephronophthisis
- Methylmalonic Acidemia
- Oxalosis
- Polycystic kidney disease (Autosomal recessive)

However, all other patients with non-glomerular diagnoses will require at least two of the following conditions. All conditions except for abnormal imaging/biopsy must have occurred after the initial 6 months of life and must not be secondary to a current or resolving episode of Acute Kidney Injury (AKI):

- o significant proteinuria,
  - Age < 2 years old: urine protein to creatinine ratio > 0.5
  - Age ≥ 2 years old: urine protein to creatinine ratio > 0.2
- o hematuria (for at least 3 months),
- evidence of renal tubular disorders,
- o abnormalities detected by kidney biopsy or imaging
- o abnormal kidney function
  - Age < 2 years old: serum creatinine > 0.4 mg/dL
  - Age  $\geq$  2 years old: eGFR < 90 ml/min|1.73m^2

(eGFR=41.3 x height[meter]/creatinine[mg/dL])

- Hypertension defined by one of the following:
  - Documented hypertension noted in the medical record by the physician
  - Current treatment of hypertension
  - Blood pressure > 95th percentile for age and gender on at least two occasions

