## 5.4 Follow-up Schedule

Approximately six hundred (600) children were enrolled over a four-year period in Cohort 1. In Cohort 2, approximately 300 children were enrolled over a two-year period. In Cohort 3, an additional 190 are expected to be enrolled. Participants enrolled in Cohort 2 followed the same contact pattern as Cohort 1. Participants were scheduled to return within 6 months of the baseline GFR assessment, depending on the age of the child and then annually for in-person follow-up visits for approximately 13 years in CKiD (i.e., through V15). Except for the GFR assessment, the neuro battery and some of the cardiovascular measurements, Cohort 3 will follow a similar contact pattern as the other cohorts. GFR assessment will be optional in cohort 3. These study visits are intended to be completed on an out-patient basis. In order to provide flexibility when scheduling study visits, each study visit may be scheduled during varying time periods. Specifically, V1a will be scheduled within one (1) year after the eligibility form is completed. V1b will be scheduled within 6 months but no more than one (1) year after V1a. The subsequent follow-up visits will be scheduled as follows:

- the first annual follow-up visit (V2) will occur one (1) year after V1a, plus or minus one month. However, if the visit is difficult to schedule, the visit can also be scheduled no more than two (2) years after V1a.
- Visit 3 will be scheduled two (2) years (± one month) after V1a or no more than three (3) years after V1a for visits that are difficult to schedule.
- Visit 4 will be scheduled three (3) years (± one month) after V1a or no more than four (4) years after V1a for visits that are difficult to schedule.

- Visit 5 will be scheduled four (4) years (± one month) after V1a or no more than five (5) years after V1a for visits that are difficult to schedule.
- Visit 6 will be scheduled five (5) years (± one month) after V1a or no more than six (6) years after V1a for visits that are difficult to schedule.
- Visit 7 will be scheduled six (6) years (± one month) after V1a or no more than seven (7) years after V1a for visits that are difficult to schedule.
- Visit 8 will be scheduled seven (7) years (± one month) after V1a or no more than eight (8) years after V1a for visits that are difficult to schedule.
- Visit 9 will be scheduled eight (8) years (± one month) after V1a or no more than nine (9) years after V1a for visits that are difficult to schedule.

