## 6.2.1.6 Proteinuria and Urine Creatinine

Recently, a variety of studies have indicated that proteinuria is an important and independent risk factor for the progression of renal disease [Besbas 1998, Bolton 2001, Brenner 2002, Misselwitz 2002, Shinohara 2002, Stenvinkel 1999]. Proteinuria has also been documented as a risk factor for progressive decline in kidney function among children with CKD [Mitsnefes 2003a, Wingen 1997]. At the baseline visit, Visit 2 and every other year thereafter, a first morning urine will be sent centrally for assessment of protein to creatinine ratio. For children who do not wear diapers, the first morning urine should be collected at home. If the first morning urine is not collected at home or if the child is a diapered child, the clinical site will obtain a spot urine. The urine collection time will be documented for all urine samples.

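### New overt proteinuria is defined as UP/Cr > 0.2 at every age, while the protocol's own proteinuria criterion under age 2 is > 0.5, so some infants are wrongly dropped as prevalent or, less often, counted as events

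*Protocol*

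**What the plan says.** Protocol section 6.2.3.2.4 makes the slope of the urine protein to creatinine ratio a secondary outcome and adds: "We will also assess for new overt proteinuria – UP/Cr > 0.2". The timed-excretion alternative given there (> 4 mg/m²/hr) also has no age condition.

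Section 4.2.1 lists significant proteinuria among the conditions that can establish CKD for Cohort 3, and splits it by age: "Age < 2 years old: urine protein to creatinine ratio > 0.5" and "Age ≥ 2 years old: urine protein to creatinine ratio > 0.2". The narrative part of the same section repeats the split.

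On ages, section 4.2 says of Cohort 3 that "we will enroll children as young as 6 months old", and of the earlier cohorts: "In Cohorts 1 and 2, children less than one year old were not enrolled".

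On timing, section 5.4 states that "the first annual follow-up visit (V2) will occur one (1) year after V1a, plus or minus one month". It allows up to two years after V1a when the visit is hard to schedule. Table 5.4.1a places central urine protein and creatinine at V1a, V2 and every later annual visit, but not at V1b. Section 6.2.1.6 is sparser after baseline: "Visit 2 and every other year thereafter, a first morning urine will be sent centrally".

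Nothing in the protocol limits the outcome to children aged 2 or older, gives it an age-specific cut-off, or explains the single value.

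**The concern.** The outcome uses the same ratio and the same 0.2 as the eligibility criterion for children aged 2 and over, but has no counterpart to the under-2 criterion. A child under 2 with a ratio of 0.3 does not meet the protocol's proteinuria criterion, yet has overt proteinuria for the outcome.

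The resulting labelling depends on age and, through entry age, partly on cohort. Comparisons of proteinuria onset by age, cohort or disease duration could pick up the definition rather than the disease. Cohort 3 was added to describe early non-glomerular disease, so its youngest members are the ones most exposed.

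**Working it through.** No sample size, power or alpha figure rests on this outcome, so there is no stated figure to reproduce. The check compares the two rules and then does arithmetic on age at visit.

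**1. Where the rules disagree** (6.2.3.2.4 against 4.2.1)

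- Under 2 years, ratio <= 0.2: below threshold under both.
- Under 2 years, ratio > 0.2 and <= 0.5: overt under 6.2.3.2.4, below threshold under 4.2.1.
- Under 2 years, ratio > 0.5: above threshold under both.
- 2 years and over: the same cut-off of 0.2 in both.

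Only the second line is in conflict.

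**2. Effect at baseline.** I read new as absent at baseline. A child in the discordant band at V1a is then prevalent and leaves the at-risk set. This requires V1a before 24 months of age: 6 to under 24 months in Cohort 3, and 12 to under 24 months in Cohorts 1 and 2. All three cohorts are exposed.

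**3. Effect at follow-up.** A false new event needs a V1a value <= 0.2 and a V2 value in the band while the child is still under 24 months.

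- Age at V2 = age at V1a + 12 months, with a window of 11 to 13 months.
- V2 on the nominal date: age at V1a < 24 − 12 = 12 months.
- V2 at the earliest date: age at V1a < 24 − 11 = 13 months.
- V2 at the latest date in the window: age at V1a < 24 − 13 = 11 months.
- V2 delayed to two years after V1a: even a child aged 6 months at V1a is 6 + 24 = 30 months old, so no false event is possible.
- Cohorts 1 and 2 enter at 12 months or later, so V2 falls at 12 + 11 = 23 months at the earliest and 24 months or later on the nominal date. Their exposure is a sliver.
- V3 for the youngest possible entrant is at about 6 + 24 = 30 months, so on the planned schedule each child has at most one follow-up value under age 2.

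The second route is therefore essentially confined to Cohort 3 children with V1a between 6 and about 12 to 13 months.

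**4. How many.** The protocol gives no count under age 2. Cohort 3 has 190 children aged 6 months to 16 years. Table 4.2 shows 99 of 586 Cohort 1 children in the 1 to 4 year stratum. Neither figure isolates children under 2, and nothing gives the share with a ratio between 0.2 and 0.5. No number can be derived.

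**5. Simply copying the age split into the outcome.** With > 0.5 before age 2 and > 0.2 afterwards, a child steady at 0.3 would become an event on passing the second birthday. The at-risk set must therefore start at age 2. Once it does, the > 0.5 part can never produce an event.

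**The case against.** The best defence is that the two cut-offs serve different purposes. The > 0.5 figure is one of six optional conditions used to confirm that CKD is present, and six named diagnoses need none of them. The protocol varies its proteinuria cut-offs elsewhere: 0.5 at all ages for the progression strata in section 9.1, and 2 in the competing-risks example in section 8.1.2. An outcome cut-off that differs from an entry criterion is not in itself an error. The add-on also sits behind a continuous slope, and how baseline status defines the at-risk set is often left to a statistical analysis plan.

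Part of this stands. It limits the importance of the point and rules out several stronger readings that a reader might infer:

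- That infants in the band are generally counted as events. Those already in it at V1a are prevalent, not new.
- That ratios of 0.2 to 0.5 under age 2 are normal or accepted. The protocol says only that they fall below its entry criterion.
- That one sample is labelled both ways. Eligibility starts from available records, and V1a may follow the eligibility form by up to a year.
- That the definition was left behind when Cohort 3 was added. Children aged 12 to 23 months were already eligible for Cohorts 1 and 2.

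What does not stand is that the difference needs no comment. The protocol itself fixes the outcome cut-off, uses an age split for the same ratio elsewhere, and neither restricts nor justifies the single value.

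**Conclusion.** The inconsistency is real and worth correcting, but it is modest. Under age 2, a ratio above 0.2 and up to 0.5 meets the outcome definition while failing the protocol's own proteinuria criterion. The wider consequence is removal from the at-risk set at baseline, possible in any cohort for entry under age 2. The narrower one is a false new event at V2, essentially limited to Cohort 3 infants with V1a before about 12 to 13 months.

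A reader might want to state a percentage of Cohort 3 misclassified. The documents do not support one, because both the share under 2 and the share in the band would have to be assumed. Such a product would also count mainly prevalent children rather than false events. The number is probably small.

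The conclusion assumes that new means absent at baseline and that visits follow section 5.4. The UP/Cr slope, the GFR outcomes and every power figure in section 9 are unaffected.

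**What to change.** Reconcile 6.2.3.2.4 with 4.2.1. State that new overt proteinuria (UP/Cr > 0.2) is assessed only from age 2, and that a child enters the at-risk set with a first value at or after age 2 that is <= 0.2. Leave the > 0.5 threshold out of the event definition. Neither an infancy value nor the second birthday can then create or remove an event. If a single cut-off at all ages is intended, the protocol should say so and give the reason.

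No new data are needed. The cost is later entry to the at-risk set for children enrolled under 2. With V1a at 6 months, V2 is at 18 months and V3 at 30 months. On the annual schedule of Table 5.4.1a, the first qualifying value is at V3 and the earliest possible event at V4 (42 months). If urine were measured only as in section 6.2.1.6 (V2, V4, V6), these would move to V4 and V6 (66 months), so the text should also say which schedule applies. Infancy values still contribute to the slope.

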#### 6.3 Neurocognitive Measures

CKiD will conduct a battery of neurocognitive assessments at the second baseline visit (V1b), and every two years thereafter through V7. Beginning at V9, the study will discontinue performing psychological assessments, which are administered by the site's psychologist (refer to Table 5.4.1a for visit pattern). In the event that the participant demonstrates neurocognitive deficits, problems or inefficiencies at study visit 7, the site should encourage the parents and nephrologist to have follow-up testing within the participant's school or community.

Age-specific neuropsychological tests will be administered to all study participants to measure areas of cognition, development and behavior; however, cognitive tests are only standardized in English. In addition to the battery of neurocognitive assessments, CKiD will employ a behavior coding mechanism that will provide examiner perception of the reliability of the test data collected and will assist in determining why a particular task was not administered or why the data should be marked in the data set because of its low reliability. This rating will be conducted for each task that is administered (e.g., subtests of larger batteries) and should be completed immediately after the task is completed. This coding system is included in Appendix C and involves a 2-point code for each task (e.g., 1.0 for a typical reliable administration).

## 6.3.1 Core Tests

Based on the availability of resources and feasibility of performing the psychological assessments, the core tests for cognitive and developmental assessment:

- Mullen Scales of Early Learning (Mullen Scales) 6 to 29 months
- Wechsler Preschool and Primary Scale of Intelligence Third Edition (WPPSI-III) – 30 months through 5 years
- Wechsler Abbreviated Scales of Intelligence Second Edition (WASI II) 6 years and older
- Conners' Kiddie Continuous Performance Test (K-CPT) 4 to 5 years
- Conners' Continuous Performance Test II (CPT-II) 6 years and older
- Delis-Kaplan Executive Function System:
  - Tower Subtest (D-KEFS Tower) 6 years and older
  - Verbal Fluency Subtest (D-KEFS Verbal) 6 years and older
  - Figural Fluency Subtest (D-KEFS Figural) 6 years and older
  - Color-Word Interference Subtest (D-KEFS Color-Word) 6 years and older
- Wechsler Intelligence Scale for Children Fourth Edition (WISC-IV) Digit Span Subtest – 6 to 16 years
- Wechlser Intelligence Scale for Children Fourth Edition Integrated (WISC-IV-I) Spatial Span Subtest – 6 to 16 years old
- Wechsler Adult Intelligence Scale Fourth Edition (WAIS-IV) Digit Span Subtest (ONLY the Forward & Reverse Components) – 17 years and older
- Wechsler Memory Scale Third Edition (WMS-III) Spatial Span Subtest 17 years and older

The core tests for behavioral assessment are:

- Behavior Assessment System for Children Second Edition (BASC-2)
  - Parental Rating Scales (BASC-PRS) 2 to 21 years
  - Self Report of Personality, College Version (BASC-SRP COL) 21 to 25 years
- Quality of Life:

•

- Pediatrics Quality of Life Scale Parent Report (PedsQL-P)
   2 to 18 years
- Pediatrics Quality of Life Scale Child Report (PedsQL-C) – 8 to 17 years
- Pediatrics Quality of Life Scale Young Adult
   18 years and older
- Behavior Rating Inventory of Executive Function
  - Preschool Version (BRIEF-P) 2 to 5 years
  - BRIEF 6 to 18 years
  - Adult Version (BRIEF-A) 18 years and older

6.3.1.1 Description of Cognitive and Developmental Assessments-Core Tests The diagram below depicts the age ranges to which each of the tests are applicable.

